14.1.7.1.2 FILE MANAGEMENT AT THE INVESTIGATOR SITE

It is the responsibility of the PI to ensure that their blinded and unblinded ISF is maintained in accordance with ICH Guidance for Industry E6 Good Clinical Practice: Consolidated Guidance, Section 8 – Essential Documents for the Conduct of a Clinical Trial. Documentation is subject to inspection by the sponsor and relevant regulatory agencies.

14.1.7.2 RECORDS RETENTION AT THE INVESTIGATOR SITE

It is a sponsor/CRO requirement that all PIs participating in clinical studies maintain detailed clinical data for 1 of the following periods:

- Country-specific requirements, or
- A period of at least 2 years following the last approval of a marketing application approved by a Regulatory Authority in an ICH region or until there are no pending or contemplated marketing applications in an ICH region, or,
- A period of 2 years after the sponsor/CRO notifies the PI that the data will not be submitted for review by any Regulatory Authority

14.1.7.3 TREATMENT OF MISSING DATA

Some data elements will be missing in this study due to subjects who withdraw from the study, subjects who are lost to follow-up, or subjects who do not complete all study visits. The completion status of each subject will be documented (e.g., completed protocol, withdrew from study, lost to follow-up, etc.). All reasonable efforts will be made by the investigator site staff to maintain contact with the subjects during their participation in the study. The study coordinator will attempt to contact any subjects who are lost to follow-up. For subjects who are unwilling to return to clinic for follow-up, the study coordinator will attempt to contact them and to collect study data from them during a telephone call or by forms sent to them through the mail.

14.1.8 PROTOCOL DEVIATIONS

This study will be conducted as described in this protocol, except for an emergency situation in which the protection, safety, and well-being of the subject requires immediate intervention, based on the judgment of the PI (or a responsible, appropriately trained professional designated by the PI).

In the event of a significant deviation from the protocol due to an emergency, accident, or mistake, the PI or designee must contact the sponsor/CRO at the earliest possible time by telephone. This will allow an early joint decision regarding the subject's continuation in the study. This decision will be documented by the PI and the sponsor/CRO. It is the responsibility of the PI and/or designated investigator site personnel to report significant protocol deviations to the IRB/IEC per their institutional procedures.

A large black rectangular redaction box covers the majority of the page content, from approximately y=113 to y=886. A thin blue horizontal line runs across the page, intersecting the redaction box. The redaction box is positioned above the blue line, and the area below the blue line is also blacked out.

14.2 ADDITIONAL CONSIDERATIONS

14.2.1 ETHICS AND RESPONSIBILITY

This study must be conducted in compliance with the protocol, the ICH Guidance for Industry E6 Good Clinical Practice: Consolidated Guidance and the applicable regulatory requirements. PIs must submit all essential regulatory documentation, as required by local and national regulations (including approval of the protocol and informed consent form by an HHS-registered IRB/IEC) to the sponsor/CRO before IP will be shipped to the investigator site.

Black box for the *liver* model.

A high-contrast, black and white image showing a dark, irregular shape on the left and a bright, jagged edge on the right, suggesting a high-contrast image of a physical object or a processed image of a scene.

— [REDACTED]

■ XXXXXXXXXX

— 1 —

For more information, contact the Office of the Vice President for Research and Economic Development at [contact] or [contact].

1 INTRODUCTION

This document details the planned statistical analyses for Revance Therapeutics, Inc. protocol “1820201” study titled “A Phase II, Prospective, Randomized, Double-Blind, Multi-center, Placebo-Controlled Trial of DaxibotulinumtoxinA for Injection for the Management of Plantar Fasciitis”.

The proposed analyses are based on the contents of the protocol amendment version 4.0 (dated 15-JUL-2019).

This is a Phase 2, randomized, double-blind placebo-controlled, multicenter study of 2 doses of DaxibotulinumtoxinA (DAXI) for injection in adult subjects with unilateral plantar fasciitis (PF).

Subjects recruited from approximately 20 investigator sites in the United States (US) will be randomized

[REDACTED]

At Week 8, in cases of no improvement, either based on the Numeric Pain Rating Scale (NPRS) score (i.e. no change or worsening of the NPRS score from baseline) or on the investigator’s clinical judgment of no clinical improvement following treatment, regardless of whether the subject showed a treatment benefit based on the NPRS score evaluation, a subject will be considered an “early study completer” and will exit the study. Week 8 will serve as the early completion visit for the subject. Subjects who experience any treatment benefit at Week 8, defined as any decrease in NPRS score from baseline, will continue to be observed up until Week 24.

2 STUDY OBJECTIVES

The objective of this study is to compare the efficacy and safety of 2 doses of DAXI for injection versus placebo for managing plantar fasciitis.

[figure not shown]

3 ENDPOINTS

3.1 Primary Endpoint

The primary efficacy endpoint is:

- Change from baseline in NPRS score, which is recorded within 15 minutes after stepping out of bed in the morning (average over 5 days, defined as 4 days prior to study visit and on the study visit day) at Week 8.

[figure not shown]
3.4 Safety Endpoints

- Frequency, severity and relationship to study drug of treatment-emergent adverse events during the first 8 weeks post treatment and the overall study duration
- Frequency, severity and relationship to study drug of treatment-emergent serious adverse events during the first 8 weeks post treatment and the overall study duration

4 SAMPLE SIZE

The sample size calculations are based on the minimal clinically important difference of 2 points for NPRS ([Farrar, 2001](#); [Michener, 2011](#)).  

5 RANDOMIZATION

Subjects that complete the screening and run-in periods and have met all inclusion and none of the exclusion criteria will be randomized 

6 PLANNED ANALYSES

No statistical analysis plan (SAP) prepared in advance of the data can be absolutely definitive and the final Clinical Study Report (CSR) may contain additional tables or statistical tests if warranted by the data obtained. The justification for any such additional analyses will be fully documented in the final CSR.

6.1 Analysis Populations

Subjects excluded from the analysis populations and the reason for their exclusion will be listed in Appendix 16.2 of the CSR.

6.1.1 Intent-to-Treat (ITT) Population

The Intent-to-Treat (ITT) population includes all subjects randomized who received study treatment, with treatment arms classified based on randomization assignment, regardless of the actual treatment received. Efficacy analysis will be performed using the ITT population.

6.1.2 Per Protocol (PP) Population

The Per Protocol (PP) population is defined as a subset of the ITT population that excludes subjects with the major protocol violations/deviations that affect safety and/or efficacy identified during the deviation review meetings

A large rectangular area of the page is completely blacked out, indicating that the original content has been redacted.

6.1.3 Safety Population

The Safety Population includes all randomized subjects who received study treatment, with treatment arms classified based on the treatment each subject actually received, regardless of randomization assignment.

6.1.4 Non-COVID-19 Impacted Population

The Non-COVID-19 Impacted Population is defined as a subset of the ITT population that excludes subjects with any COVID-19-related protocol deviations.

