6.1.5 Completed Subject

Study completion may occur at Week 8 or at Week 24. Thus, there will be two types of completers in the study, and they are as follows:

- Week 8 Early Study Completers: subjects who do not demonstrate improvement at Week 8, either based on the NPRS score (i.e. no change or worsening of the NPRS score from baseline) or on the investigator's clinical judgment of no clinical improvement following treatment, regardless of whether the subject showed a treatment benefit based on the NPRS score evaluation. These subjects complete the study at Week 8. Assessments for Week 8 visit are recorded under the Week 24/ET visit for these subjects. However, for the analysis, this will be remapped back to Week 8 visit.
- Week 24 Study Completers: subjects who demonstrate improvement at Week 8, defined as any decrease from baseline on NPRS score, and continued in the study for follow-up until conclusion of Week 24 visit.

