6.5 Protocol Deviations

Protocol deviations will be classified as Major, Minor and by Criticality. Additionally, any COVID-19-related protocol deviations will be identified. Protocol deviation categories will be

tabulated by treatment group and classification for the Safety Population. The number of subjects impacted by COVID-19, that is, with any COVID-19-related protocol deviation, number of subjects with missed visits, delayed visits, with visits performed remotely, and with missed assessments will be summarized by treatment group for the Safety Population. A listing of critical and major protocol deviations, as well as COVID-19 related protocol deviations will be provided within Appendix 16.2 of the CSR.

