6.11.1 Primary Endpoint

[figure not shown]
The primary efficacy endpoint is the change from baseline in the NPRS score, which is recorded within 15 minutes after stepping out of bed in the morning and averaged over 5 days (defined as 4 days prior to study visit and on study visit day) at Week 8.

[figure not shown]
The NPRS is a segmented numeric version of the visual analog scale (VAS) in which a respondent selects a whole number (0–10 integers) that best reflects the intensity of his/her pain. The common format is a horizontal bar or line. Similar to the VAS, the NPRS is anchored by terms describing pain severity extremes with a score of 0 representing "no pain" and a score of 10 representing "worst pain imaginable" or "pain as bad as you can imagine".

A large rectangular area of the page is completely blacked out, indicating that the content has been redacted for confidentiality.

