6.11.2 Primary Efficacy Analysis

The primary efficacy endpoint will be analyzed using the ITT population.

A large rectangular area of the page is completely blacked out, indicating that the content has been redacted for confidentiality.

[figure not shown]

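### The Non-COVID-19 Impacted Population has no time window, so using it for a Week 8 endpoint would remove Week 8 improvers selectively

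*SAP*

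**What the plan says.** **The population.** SAP 6.1.4 defines it as a "subset of the ITT population that excludes subjects with any COVID-19-related protocol deviations". The sentence is complete and gives no time window. SAP 6.5 likewise counts as impacted any subject with a COVID-19-related deviation. In the same summary it reports the "number of subjects with missed visits, delayed visits, with visits performed remotely, and with missed assessments", again with no cut-off at Week 8.

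**Who leaves at Week 8.** Under SAP 6.1.5, Week 8 early completers are subjects with no change or a worsening in NPRS, or with no clinical improvement in the investigator's judgment. The SAP says: "These subjects complete the study at Week 8". The judgment route applies "regardless of whether the subject showed a treatment benefit based on the NPRS score evaluation", so some NPRS improvers may leave as well. Protocol 8.7 says the same.

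**Who stays.** The SAP introduction says that benefit at Week 8 is "defined as any decrease in NPRS score from baseline, will continue to be observed up until Week 24". No stated route keeps an NPRS non-improver in the study.

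**The endpoint and its population.** SAP 6.11.1 states: "The primary efficacy endpoint is the change from baseline in the NPRS score", taken as a 5-day average at Week 8. SAP 6.11.2 states: "The primary efficacy endpoint will be analyzed using the ITT population".

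**The concern.** The rule that decides who is followed after Week 8 uses the sign of the same NPRS change that forms the primary endpoint. A population flag that also counts events after Week 8 therefore depends on the outcome.

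Take two subjects with complete and valid Week 8 diaries. One improved, stays in, and misses the Week 16 visit because of COVID-19: that subject is excluded. The other did not improve, left at Week 8 and cannot be excluded for that reason. The missed Week 16 visit can have had no effect on a diary average completed eight weeks earlier.

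A supportive analysis is meant to show that COVID-19 disruption did not drive the Week 8 result. If its population is selected on that result, agreement with the ITT analysis is harder to interpret, and usable Week 8 data are left out of the supportive set.

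**Working it through.** The plan gives no figure on this point to reproduce. The check has two parts: who is exposed to exclusion, and what the exclusion does to the Week 8 comparison.

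**1. Exposure to exclusion**

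Protocol 12.1.4 lists eight post-dose visits: Weeks 1, 2, 4 and 8, then 12, 16, 20 and 24. A Week 8 exiter has four visits at which a COVID-19 deviation can arise, and a Week 24 completer has eight. Let c be the chance of a deviation per visit (assumed, and independent between visits). The chance of exclusion is 1 - (1 - c)^4 or 1 - (1 - c)^8.

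| c (assumed) | Week 8 exiter | Week 24 completer |
|---|---|---|
| 2% | 7.8% | 14.9% |
| 5% | 18.5% | 33.7% |
| 10% | 34.4% | 57.0% |

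**2. Effect on a Week 8 comparison**

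Assumptions, none of them given in the visible documents:
- The Week 8 change X is normal with SD 2.5 and mean -3 on drug and -2 on placebo.
- Every subject with X < 0 continues, and a fraction q of them has a COVID-19 deviation after Week 8.
- Deviations up to Week 8 are unrelated to outcome.

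Formulas, for mean m and SD s:
- p = P(X < 0) = Φ(-m/s)
- E(X | X < 0) = m - s·φ(m/s)/p
- E(X | X ≥ 0) = m + s·φ(m/s)/(1 - p)
- Share retained = p(1 - q) + (1 - p)
- Retained mean = [p(1 - q)·E(X | X < 0) + (1 - p)·E(X | X ≥ 0)] / share retained

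Drug: p = 0.885, E(X | X < 0) = -3.55, E(X | X ≥ 0) = 1.22. Placebo: p = 0.788, with -2.92 and 1.42.

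At q = 0.4:
- Drug: the share retained is 0.885 × 0.6 + 0.115 = 0.646. The retained mean is (0.531 × -3.55 + 0.115 × 1.22)/0.646 = -2.70.
- Placebo: the share retained is 0.788 × 0.6 + 0.212 = 0.685. The retained mean is (0.473 × -2.92 + 0.212 × 1.42)/0.685 = -1.58.
- Difference: -2.70 - (-1.58) = -1.12.

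| q (assumed) | Drug mean | Placebo mean | Difference | Retained, drug / placebo |
|---|---|---|---|---|
| 0 | -3.00 | -2.00 | -1.00 | 100% / 100% |
| 5% | -2.97 | -1.96 | -1.01 | 96% / 96% |
| 10% | -2.95 | -1.92 | -1.03 | 91% / 92% |
| 20% | -2.88 | -1.83 | -1.05 | 82% / 84% |
| 40% | -2.70 | -1.58 | -1.12 | 65% / 68% |
| 60% | -2.38 | -1.18 | -1.20 | 47% / 53% |

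**3. Other settings**

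- *True difference of 2 points*, the figure behind the sample size in SAP 4, with means -4 and -2 and SD 2.5: the difference becomes -2.10 at q = 20% and -2.44 at q = 60%.
- *SD 2 to 3 and placebo mean -1 to -3*, true difference -2.00: -2.02 to -2.05 at q = 10%, -2.09 to -2.17 at 30%, and -2.20 to -2.34 at 50%.
- *No true difference, equal q:* the arm means still shift, but the difference stays at 0.00.
- *No true difference, unequal q:* with both means at -2, q = 20% in one arm and 30% in the other gives -1.83 and -1.72, a spurious difference of 0.11.

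**4. With a Week 8 cut-off**

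If only deviations up to Week 8 count, and they are unrelated to outcome, the retained means equal the true means and the difference is unbiased.

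**The case against.** The strongest reply is that no visible text applies this population to a Week 8 endpoint, or to any analysis. The primary analysis is on ITT. The one visible sensitivity analysis (SAP 6.11.3.1) uses the Per Protocol population, and the pages after it are redacted. The subject disposition summary in SAP 6.4 lists only Safety, ITT and PP. Redacted text could add a date limit or use the set only for later time points. This stands: the definition is certain, but its effect on a Week 8 result is conditional.

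The second reply is about size, and much of it stands. The documents give no rate of COVID-19 deviations. At 5% to 10% a true difference of -1.00 moves by only 0.01 to 0.03. With an assumed 50 subjects per arm and SD 2.5, the standard error of a difference is 2.5 × √(2/50) = 0.50, so even the shift of 0.12 at 40% is small beside sampling error. The working also compares raw means rather than the site- and baseline-adjusted ANCOVA of Protocol 13.3.2, and it ignores NPRS improvers who leave on investigator judgment. That route softens the selection without removing it.

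A reader might infer that the Per Protocol analysis of the Week 8 endpoint has the same fault. The documents do not support that. The visible definition "excludes subjects with the major protocol violations/deviations that affect safety and/or efficacy identified during the deviation review meetings", which is much narrower than any COVID-19 deviation, and it runs into a redacted block that may contain a time limit. A missed Week 16 visit is not shown to be a major deviation of that kind.

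A reader might also infer that the primary result is biased, or that the rule could manufacture an effect. The primary analysis does not use this set. With equal arms and equal deviation rates the between-arm bias is zero.

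**Conclusion.** The point holds for SAP 6.1.4 as written. The definition has no time window, and exposure to exclusion after Week 8 depends on the sign of the Week 8 NPRS change. If the set is used for a Week 8 endpoint, both arm means move towards less improvement, and a true difference is mildly exaggerated in favour of drug when the arms share the same deviation rate.

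In the illustration a true -1.00 becomes about -1.03, -1.05 and -1.12 at 10%, 20% and 40%. These figures rest on an assumed SD, assumed arm means, assumed deviation rates, and deviations before Week 8 being unrelated to outcome. The direction of the shift in the arm means follows from the design; its size does not.

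This is a flaw in a supportive population, worth correcting because the correction is easy. It is no threat to the ITT primary analysis, and it is not a finding about the Per Protocol population.

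**What to change.** In SAP 6.1.4, tie the population to the endpoint's time point:

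- For Week 8 endpoints, exclude only ITT subjects with a COVID-19-related deviation on or before the Week 8 visit. If that visit was missed, the expected visit date already defined in SAP 6.11 can serve as the cut-off.
- Let later deviations exclude subjects only from analyses after Week 8.
- In the SAP 6.5 summary, show COVID-19 deviations by timing (up to or after Week 8), arm and completer type, so that a reader can judge how much the cut-off matters.

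If redacted text already restricts the window, 6.1.4 should say so.

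The cost is a sentence in the SAP, a date condition on the population flag and one more breakdown in an existing table. No new data are needed, the supportive set keeps more subjects for Week 8, and the primary analysis does not change.

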6.1.5 Completed Subject

Study completion may occur at Week 8 or at Week 24. Thus, there will be two types of completers in the study, and they are as follows:

- Week 8 Early Study Completers: subjects who do not demonstrate improvement at Week 8, either based on the NPRS score (i.e. no change or worsening of the NPRS score from baseline) or on the investigator's clinical judgment of no clinical improvement following treatment, regardless of whether the subject showed a treatment benefit based on the NPRS score evaluation. These subjects complete the study at Week 8. Assessments for Week 8 visit are recorded under the Week 24/ET visit for these subjects. However, for the analysis, this will be remapped back to Week 8 visit.
- Week 24 Study Completers: subjects who demonstrate improvement at Week 8, defined as any decrease from baseline on NPRS score, and continued in the study for follow-up until conclusion of Week 24 visit.

6.2 Derived Data

This section describes the derivations required for statistical analysis. Unless otherwise stated, variables derived in the source data will not be re-calculated.

6.2.1 Race

Where more than one race category has been selected for a subject, these race categories will be combined into a single category labeled "Multiple" in the summary tables. The listings will reflect the original selected categories.

6.2.2 Baseline

Unless otherwise specified, baseline is defined as the last non-missing value (either scheduled, unscheduled or repeat) before the subject receives the dose of study drug at Day 1. For re-screened subjects, if assessment was not done on the second screening, the initial screening result will be considered.

6.2.3 Duration/Study Day/Time

Study day will be calculated as the number of days from the date of dosing of study drug.

- date of event – date of dosing of study drug + 1, for events on or after dosing of study drug
- date of event – date of dosing of study drug, for events before dosing of study drug.

[figure not shown]
For all time to event analyses, subjects not reporting the specified endpoint will be censored at the time that the subjects were last known not to have experienced the endpoint. In complex

[figure not shown]

WORLDWIDE CLINICAL TRIALS
SCIENTIFICALLY MINDED • MEDICALLY DRIVEN

Revance Therapeutics, Inc.
1820201
Statistical Analysis Plan
Version 1.0
Issue Date 04-SEP-2020

cases where the censoring time of the subject is uncertain, the case will be reviewed by the Worldwide Statistician and a censoring time will be assigned before database lock.

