8.7 END OF STUDY DEFINITION

Study completion may occur at Week 8 (“early study completers” who have no treatment benefit based on NPRS) or at Week 24 (“study completers”):

Week 8 Early Study Completers:

- No Treatment Benefit:
 - Subjects who do not demonstrate improvement at Week 8, where improvement is defined as any decrease from baseline on NPRS score
 - A subject may also complete the study at Week 8 based on the investigator’s clinical judgment of no clinical improvement following treatment, regardless of whether the subject showed a treatment benefit based on the NPRS score evaluation described above.

Week 24 Study Completers:

- Treatment Benefit: Subjects who demonstrate improvement at Week 8, defined as any decrease from baseline on NPRS score, should continue in the study for follow-up until Week 24 and will be considered “complete” following the conclusion of their Week 24 visit.

For subjects who choose to discontinue from the study prior to these timepoints for any reason, every effort should be made to complete the Week 24/ET visit.

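### The general censoring rule has no visible exception for outcome-driven Week 8 exits, so improvement-type time-to-event estimates past Week 8 would rest on informative censoring

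*SAP*

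**What the plan says.** **Censoring.** In the readable text of SAP 6.2.3, one rule covers every time-to-event analysis and censors anyone without the event at the last moment they were known to be free of it: "For all time to event analyses, subjects not reporting the specified endpoint will be censored at the time that the subjects were last known not" (the sentence runs on). It carries no reservation of the kind that opens SAP 6.2.2 or qualifies the NPRS rules in SAP 6.11. The only visible exception concerns complex "cases where the censoring time of the subject is uncertain, the case will be reviewed by the Worldwide Statistician", who assigns a time before database lock.

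**Length of follow-up.** Protocol 8.7 makes Week 8 the planned end of study for "Subjects who do not demonstrate improvement at Week 8, where improvement is defined as any decrease from baseline on NPRS score". It also lets the investigator end participation at Week 8 on a judgment of no clinical improvement, "regardless of whether the subject showed a treatment benefit based on the NPRS score evaluation described above". SAP 6.1.5 gives the same two routes, describing early completers as "subjects who do not demonstrate improvement at Week 8, either based on the NPRS score" or on clinical judgment, and adds: "These subjects complete the study at Week 8". For the rest, SAP 1 says: "Subjects who experience any treatment benefit at Week 8, defined as any decrease in NPRS score from baseline, will continue to be observed", up to Week 24.

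**Early completers elsewhere in the SAP.** They are defined (6.1.5), their exit assessments are mapped back to Week 8 (6.2.9), and they are counted in disposition (6.4). The censoring rule does not mention them.

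**What cannot be read.** The time-to-event endpoints, their estimators and their time horizons are not visible. SAP 6.2.4 to 6.2.6 and most of 6.11 after 6.11.3.1 are blacked out or not shown.

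**The concern.** Kaplan-Meier and related methods treat a censored subject as having the same future risk as those still under observation. Here planned follow-up is cut short because of the efficacy outcome. After Week 8 the risk set consists mostly of subjects selected for having improved, and the curve gives their later course to those who left. The groups can differ in another way too: stayers with less than a 20% NPRS reduction may receive physical therapy from Week 8 (Protocol 10.6.1).

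At stake is any reported proportion improved or responding by Week 24, and any comparison of arms built on it. If exit rates differ by arm, or late event rates do, the contrast is affected as well as the level.

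**Working it through.** **No planned figure to reproduce.** The readable text gives no event rate, hazard ratio or power for a time-to-event analysis. The total of about 150 subjects belongs to the Week 8 mean-change endpoint. All probabilities below are assumptions for an endpoint such as time to improvement.

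**Does the exception apply?** It is for uncertain censoring times. A planned Week 8 exit has a known date, so read literally the rule censors an event-free early completer at that date.

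**Notation, per arm.**
- S8: event-free share at Week 8
- e: share of the arm exiting event-free at Week 8
- h: event probability from Week 8 to Week 24 among event-free subjects who stay
- h0: the same probability among those who exit

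With no other censoring:
- Week 24 incidence under the present rule = 1 - S8(1 - h)
- True incidence = 1 - [(S8 - e)(1 - h) + e(1 - h0)]
- Bias = e(h - h0)

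**Check of the formula.** Take S8 = 0.6, e = 0.3, h = 0.5, h0 = 0. The present rule gives 1 - 0.6 x 0.5 = 0.70 (simulation: 0.701). The true value is 1 - (0.3 x 0.5 + 0.3) = 0.55. The bias is 0.15 = 0.3 x 0.5.

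**Size within an arm.**

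| e | h | bias if h0 = 0 | bias if h0 = h/2 | bias if h0 = h |
|---|---|---|---|---|
| 0.10 | 0.2 | 2 points | 1 point | 0 |
| 0.20 | 0.5 | 10 points | 5 points | 0 |
| 0.40 | 0.5 | 20 points | 10 points | 0 |

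**Effect on the arm difference (h0 = 0).** The bias in active minus placebo is e_A h_A - e_P h_P.

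1. *Understated.* S8 = 0.5 active and 0.7 placebo, e = 0.15 and 0.30, h = 0.3 in both.
   - Present rule: 1 - 0.5 x 0.7 = 65% and 1 - 0.7 x 0.7 = 51%, a difference of 14 points.
   - Exits as non-events: 0.50 + 0.35 x 0.3 = 60.5% and 0.30 + 0.40 x 0.3 = 42%, a difference of 18.5 points.
2. *Overstated.* Same S8 and e, but h = 0.5 active and 0.2 placebo.
   - Present rule: 1 - 0.5 x 0.5 = 75% and 1 - 0.7 x 0.8 = 44%, a difference of 31 points.
   - Exits as non-events: 0.50 + 0.35 x 0.5 = 67.5% and 0.30 + 0.40 x 0.2 = 38%, a difference of 29.5 points.
   - The arms are inflated by 7.5 and 6.0 points, so the difference is 1.5 points too large.
3. *Unaffected.* Same S8, e = 0.20 and h = 0.4 in both arms.
   - Present rule: 70% and 58%, a difference of 12 points.
   - Exits as non-events: 62% and 50%, again 12 points. Each arm is still inflated by 8 points.

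**The case against.** The strongest answer is that nobody outside the sponsor can see the analyses concerned. No readable section names a time-to-event endpoint or plans an estimate past Week 8, and the general rule sits in a section on derived data. Endpoint definitions with their own censoring rules could well be in the redacted pages. This stands: one can say that no exception is visible, not that none exists.

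The objection also defeats several stronger readings that a reader might infer.

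- *That every survival estimate after Week 8 is biased.* The mechanism needs an endpoint that can first occur after Week 8. For loss of benefit, non-improvers may already have had the event or may never enter the risk set. Without the definition, no rule for such an endpoint can be proposed.
- *That the treatment effect is understated.* This follows only if placebo has more event-free exits and late event probabilities are similar. The second example in the working reverses the direction with the same exit shares.
- *That all early completers are NPRS non-improvers.* The investigator's route allows exit despite an NPRS decrease. Such a subject may already have had the event and so would not be censored. Those still event-free leave for judged lack of improvement, so their censoring remains tied to outcome.

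Finally, counting exits as non-events replaces one untestable assumption (h0 = h) with the opposite extreme (h0 = 0). That is fair, and it is a reason to report both. It does not make the present rule neutral.

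**Conclusion.** The point holds conditionally. On the readable text, SAP 6.2.3 censors event-free Week 8 early completers at an exit that lack of improvement triggers. For any improvement or response endpoint extending past Week 8 and not covered by its own rule, each arm's Week 24 incidence is biased by e(h - h0). The bias is upward whenever stayers have the higher late event probability. Over the assumed values in the table it runs from 0 to 20 points. The documents supply none of e, h or h0, so this is a range, not an estimate for the trial.

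The bias in the arm difference has no fixed sign. It is zero when exit shares and late event probabilities (h and h0) are equal across arms. Time-to-event estimates up to Week 8 and the primary Week 8 mean-change analysis are not affected. The rule should be settled before database lock, because a choice made after unblinding would be open to challenge.

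**What to change.** In SAP 6.2.3, add a rule for improvement-type endpoints that extend past Week 8, to apply unless an endpoint-specific rule already covers early completers (in which case a cross-reference is enough):

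- Treat Week 8 early-completer exit without the event as a competing event and report cumulative incidence. Keeping the subject in the risk set as a non-event to Week 24 gives the same figure when there is no other censoring.
- Keep censoring at last observation for ordinary withdrawals.
- Keep the present rule for early completers as a sensitivity analysis.

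The cost is a few lines of SAP text and one additional run per endpoint, with no change to trial conduct. The downside is small: read as the proportion improved by Week 24, the new analysis assumes that early completers would not improve later (h0 = 0). The retained analysis shows the other extreme (h0 = h), so the two together show how much depends on this assumption.
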